## **Appendix 4      Examples of SGLT2 Inhibitors**

The following medications are prohibited during the study. Other medications containing SGLT2 inhibitors that may become approved for the treatment of T2DM during the THR-1442-C-603 study will also be prohibited in this study.

Generic Name	Trade Name
canagliflozin	Invokana™
canagliflozin plus metformin	Invokamet™
dapagliflozin	Farxiga™ or Forxiga™
empagliflozin	Jardiance®
empagliflozin plus linagliptin	Glyxambi®

---

## **Appendix 5      Examples of Medications with Hypotensive Effects**

Class of Medications	Indication	Example
Diuretics	heart failure associated edema	furosemide, hydrochlorothiazide
Alpha blocker	prostate enlargement	prazosin, terazosin
Beta blocker	angina, tachycardia	atenolol, propranolol
Dopamine agonist	Parkinson's disease	pramipexole, levodopa
Tricyclic antidepressants	Depression	doxepin, imipramine
Phosphodiesterase inhibitor	Erectile dysfunction	sildenafil, tadalafil

## Appendix 6 KDOQI Chronic Kidney Disease Classification and Acute Kidney Injury Stage Definition

Chronic kidney disease (CKD) is defined as either kidney damage or GFR < 60 mL/min/1.73 m^3 for ≥3 months. Kidney damage is defined as pathologic abnormalities or markers of damage, including abnormalities in blood or urine tests or imaging studies ([NFK KDOQ guidelines](#)).

Stages of CKD are outlined in Table 2.

KDOQI CKD Stages		
Stage	Description	GFR (mL/min/1.73 m  )
1	Kidney damage with normal or ↑↓GFR	≥ 90
2	Kidney damage with mild ↓GFR	60-89
3	Moderate ↓GFR	30-59
4	Severe ↓GFR	15-29
5	Kidney failure	< 15 (or dialysis)

Acute kidney injury stages based on the Definition by the Acute Kidney Injury Network (AKIN) are outlined in Table 3 ([KDIGO Clinical Practice Guideline for AKI, 2012](#)).

**Table 3. Classification/Staging System for Acute Kidney Injury**

Stage	Serum creatinine criteria	Urine output criteria
1	1.5 to 1.9 times baseline or ≥ 0.3 mg/dL (≥ 26.5 μmol/L) increase from baseline	<0.5 mL/kg/h for 6 to 12 h
2	2.0 to 2.9 times baseline	< 0.5 mL/kg/h for ≥ 12 h
3	3.0 times baseline, or Increase in serum creatinine to ≥4.0 mg/dL (≥ 353.6 μmol/L), or Initiation of renal replacement therapy, or In patients < 18 years, decrease in eGFR to < 35 mL/min per 1.73 m 	< 0.3 mL/kg/h for ≥ 24 h or anuria for ≥ 12 h

1. GLOSSARY OF ABBREVIATIONS

Abbreviation	Description
ABPM	Ambulatory blood pressure monitoring
AE	Adverse Event
ALB	Albumin
ALK-P	Alkaline Phosphatase
ALT	Alanine Aminotransferase
AST	Aspartate Aminotransferase
ANCOVA	Analysis of Covariance
ATC	Anatomical Therapeutic Chemical
BMI	Body Mass index
BP	Blood Pressure
BUN	Blood Urea Nitrogen
Ca	Calcium
CEC	Cardiovascular Endpoint Committee
CI	Confidence Interval
Cl	Chloride
CRF	Case Report Form
dL	Deciliter
DMC	Data Monitoring Committee
ECG	Electrocardiogram
ET	Early Termination
eGFR	Estimating Glomerular Filtration Rate
GMI	Genital Mycotic Infection
HbA1c	Hemoglobin A1c
Hct	Hematocrit
HDL-C	High Density Lipoprotein Cholesterol
Hgb	Hemoglobin

Abbreviation	Description
ICH	International Conference on Harmonization
ITT	Intention-to-Treat
IWRS	Interactive Web Response System
LDL-C	Low Density Lipoprotein Cholesterol
MACE	Major Adverse Cardiovascular Event
MCH	Mean Cell Hemoglobin
MCHC	Mean Cell Hematocrit
MCV	Mean Cell Volume
Max	Maximum
MedDRA	Medical Dictionary for Regulatory Activities
Mg	Milligram
MI	Myocardial Infarction
Min	Minimum
mL	Milliliter
NA	Not Applicable
Na	Sodium
PP	Per Protocol
PR	Time from the beginning of the P wave to the beginning of the QRS complex in electrocardiogram
PT	Preferred Term
QRS	Graphical deflections corresponding to ventricular depolarization in a typical electrocardiogram
QTc	Time between the start of the Q wave and the end of the T wave in the ECG, corrected for heart rate
RBC	Red Blood Cell
RR	Time between the start of one R wave and the start of the next R wave in the ECG
SAE	Serious Adverse Event
SAP	Statistical Analysis Plan
SBP	Systolic Blood Pressure

Abbreviation	Description
SD	Standard Deviation
SE	Standard Error
SI	Standard International System of Units
SOC	System Organ Class
SOP	Standard Operating Procedure
T2DM	Type 2 Diabetes Mellitus
TC	Total Cholesterol
TEAE	Treatment Emergent Adverse Event
TG	Triglycerides
TLF	Table, Listing And Figure
UTI	Urinary Tract Infection
WBC	White Blood Cell
WHO-DD	World Health Organization Drug Dictionary

2. PURPOSE

The purpose of this statistical analysis plan (SAP) is to ensure that the data listings, summary tables and figures that will be produced, and the statistical methodologies that will be used, are complete and appropriate to allow valid conclusions regarding the study objectives. Population pharmacokinetic assessments obtained for the study will be integrated with other studies, and will not be independently analyzed. A separate analysis plan details the integrated analysis methods.

2.1. RESPONSIBILITIES

Theracos has designed the study protocol and is responsible for the conduct of the study. INC Research is responsible for the development and validation of a clinical database using the MediData RAVE platform.

INC Research will perform the statistical analyses and is responsible for the production and quality control of all tables, figures and listings.

Adverse events that have met the seriousness criteria defined in the protocol are reported on the serious adverse event (SAE) forms using the MediData RAVE platform. An SAE case consists of the information reported in the SAE forms, subject characteristics documented in the case report forms, and additional source data such as hospital discharge summaries. Each SAE case is recorded in a validated ARGUS database which is managed by Covance. Any discrepancies in critical data fields of each SAE will be reconciled between the ARGUS and THR-1442-C-603 clinical database prior to database lock. The SAE coding, analyses and summaries are based on the final study data recorded in the clinical database. Detailed serious adverse event follow-up data will be reported from the ARGUS database and are not included in this report.

Theracos will perform review of all tables, figures and listings before the finalization.

2.2. TIMINGS OF ANALYSES

An interim non-binding futility analysis is planned when 50% of the randomized subjects (i.e., 300) have completed 12 weeks of double blind treatment in study 603A.

The final analysis of safety and efficacy is planned after all subjects complete the planned 36 weeks of blinded study treatment or terminate early from the studies.

3. STUDY OBJECTIVES

3.1. STUDY 603A

In study 603A, the effectiveness of bexagliflozin tablets, 20 mg, will be assessed in a study population randomized 1:1 to receive either active agent or placebo.

3.1.1. Primary Objective

The primary endpoint will be the change from baseline (Day 1) to week 12 of the average ambulatory systolic blood pressure (SBP) of the bexagliflozin group compared to the placebo group.

3.1.2. Secondary Objectives

Secondary objectives based on mean ambulatory SBP:

- The proportion of subjects who achieve a reduction of mean ambulatory SBP of 10 mm Hg or greater;
- The proportion of subjects who achieve a mean ambulatory SBP of 135 mm Hg or less at week 12;
- The maximum and minimum treatment effect (trough-to-peak ratio) by Ambulatory blood pressure monitoring (ABPM) SBP at week 12.

Secondary objectives based on seated office SBP:

- The placebo-adjusted change from baseline to week 12 in seated office SBP;
- The proportion of subjects who achieve a mean seated office SBP of 140 mm Hg or less at week 12.

Secondary objectives based on mean ambulatory diastolic blood pressure (DBP):

- The placebo-adjusted change in mean ambulatory DBP from baseline to week 12;
- The proportion of subjects who achieve a mean ambulatory DBP of 87 mm Hg or less at week 12;
- The proportion of subjects who achieve a reduction of mean ambulatory DBP of 4 mm Hg or greater at week 12.

Secondary endpoints based on seated office DBP

- The placebo-adjusted change from baseline to week 12 in seated office DBP;
- The proportion of subjects who achieve a mean seated office DBP of 90 mm Hg or less at week 12.

3.2. STUDY 603B

In study 603B, the effectiveness of bexagliflozin tablets, 20 mg, will be assessed by measurement of the loss of the treatment effect following randomized withdrawal. All study entrants will first be dosed with bexagliflozin tablets, 20 mg, for 12 weeks. At week 12 the participants will undergo a 1:1 randomization to bexagliflozin tablets, 20 mg, or placebo.

3.2.1. Primary Objective

The primary endpoint will be the change from week 12 to week 24 of the mean ambulatory SBP of the bexagliflozin group compared to the placebo group.

3.2.2. Secondary Objectives of Study 603B

The secondary objectives of study 603B are based on assessments of effects on mean ambulatory and seated office systolic and diastolic blood pressures from week 12 to week 24. These will include:

- The placebo-adjusted change from week 12 to week 24 in seated office SBP;
- The placebo-adjusted change from week 12 to week 24 in ambulatory DBP;
- The placebo-adjusted change from week 12 to week 24 in seated office DBP;

Study 603B will also include a population pharmacokinetic assessment between weeks 6 and 12, when all participants will be receiving bexagliflozin tablets, 20 mg.

Population pharmacokinetic assessments obtained for the study will be integrated with other studies, and will not be independently analyzed. A separate analysis plan details the integrated analysis methods

3.3. INTEGRATIVE OBJECTIVES OF STUDY 603A AND 603B

- To assess consistent effects on mean ambulatory SBP/DBP after 12 weeks of bexagliflozin treatment, as well as longer treatment periods, i.e., 24 weeks or 36 weeks of bexagliflozin treatment.
- The seated office systolic and diastolic blood pressure will be collected at more frequent intervals than for ambulatory monitoring, and the changes over time will be evaluated to provide a composite profile of treatment effect as a function of time.

3.4. SAFETY OBJECTIVES

The integrated safety objectives will assess the hazard ratio for adverse events associated with bexagliflozin exposure compared to placebo in all segments of both

studies in which a placebo-exposed cohort is present. The safety objectives of the study are:

- To determine the frequency and severity of treatment emergent adverse events
- To determine the frequency and severity of treatment emergent adverse events of special interest
- To record and evaluate concomitant medication use
- To evaluate any potentially adverse changes in laboratory test values
- To assess changes in cardiac rhythm through 12-lead ECG
- To evaluate vital signs
- To assess general health detected by physical examination

3.5. BRIEF DESCRIPTION

THR-1442-C-603 is an integrated assessment of the potential utility of bexagliflozin tablets, 20 mg, for the treatment of essential hypertension. It is composed of two studies, 603A and 603B, measuring effects in a common population.

3.5.1. Study 603A

Study 603A is a double blind, placebo controlled multi-center study. Approximately 680 male and female adult subjects with an office sitting blood pressure ≥ 140 mm Hg and < 180 mm Hg, and who are taking no more than 4 anti-hypertensive medications will be enrolled in study 603A. The overall population should be selected to contain $> 10\%$ of subjects with a baseline ABPM > 160 mm Hg and $< 30\%$ of subjects with type 2 diabetes mellitus.

Subjects who meet the eligibility criteria at the screening visit (visit 1) will start a 2 week run-in period. At the end of the run-in period, subjects who have not been disqualified will be eligible for participation. At the investigative site the subjects will take the last dose of run-in drug, will be fitted with an ABPM device and will start a 24-h ABPM to establish the baseline ABPM SBP and DBP. On the following day, qualified subjects who have completed the 24-h ABPM with a mean 24-h SBP ≥ 135 mm Hg will be randomly assigned to receive bexagliflozin tablets, 20 mg or placebo, using an interactive web response system (IWRS). If < 64 BP readings are recorded, the ABPM must be repeated within 2 days. Prior to randomization, subjects who cannot successfully complete the ABPM within two attempts will be considered screen failures.

A six week visit to the investigational site will allow seated office measures of systolic and diastolic BP to be recorded. At week 12 (end of study), the subject will visit the investigational site, consume the final tablet, and be fitted for ABPM.

An interim non-binding futility analysis is planned when 50% of the randomized subjects (i.e., 300) have completed study 603A.

3.5.2. Study 603B

Upon returning to the investigational site to return the ambulatory monitor at the conclusion of study 603A, subjects will begin participation in study 603B. They will receive a 12-week supply of bexagliflozin tablets, 20 mg.

At week 6 subjects will return to the investigational site for measurement of seated systolic and diastolic blood pressures. At week 12, subjects will visit the investigational site to consume the final tablet and to be fitted with an ambulatory monitor to record their baseline mean ambulatory blood pressure.

The following day, subjects will be randomized 1:1 to receive a 12-week supply of bexagliflozin tablets, 20 mg or bexagliflozin tablets, placebo.

An assessment of bexagliflozin population pharmacokinetics will also be conducted to include approximately 200 subjects. Samples will be taken between weeks 6 and 12. The population PK study design and analysis plan will be described in a designated study protocol and the analysis will be reported separately.

3.6. SUBJECT SELECTION

The study population for the integrated program will include approximately 680 subjects with essential hypertension. Eligible subjects who consent to participate in the study will be enrolled in clinical investigational sites in the United States. Study subjects will be informed of the purpose of the program, the potential risks of participation in both studies, and will be requested to consent to the procedures and blood collection on a single consent form.

Plasma samples will be collected for population PK analysis in study 603B. Study subjects will be informed of the purpose of the PK study and requested to consent to the additional procedures and blood collection.

3.6.1. Inclusion Criteria

Refer to protocol section 4.2 for inclusion criteria.

3.6.2. Exclusion Criteria

Refer to protocol section 4.3 for exclusion criteria.

3.7. DETERMINATION OF SAMPLE SIZE

The primary efficacy endpoint of study 603A is the change from baseline (Day 1) to week 12 in the 24-hour average SBP of the bexagliflozin group compared to the placebo group using superiority testing at an overall two-sided 0.05 level of significance.

The primary efficacy endpoint of study 603B is the change from week 12 to week 24 in the 24-hour average SBP in the bexagliflozin group compared to the placebo group using superiority testing at an overall two-sided 0.05 level of significance.

Although the patient population was anticipated to be nearly identical between the two studies, they were to be carried out as independent investigations with respect to their individual primary and secondary endpoints. The assumptions used to estimate the sample size for the primary endpoint of study 603A were:

1. The magnitude of the decrease from baseline (Day 1) to week 12 of the 24 h mean SBP in the bexagliflozin treatment arm will exceed that found in the placebo arm by 5 mm Hg;
2. The standard deviation of the change from baseline to week 12 will be 15 mm Hg for both the active and placebo groups;
3. The two-sided significance level is 0.05.

The assumptions to estimate the sample size required for the primary endpoint of study 603B were:

1. Bexagliflozin will remain effective for at least 24 weeks. The 24-hour average ABPM SBP will not change between Week 12 and Week 24.
2. Subjects who are randomized to receive placebo will show an increase in ABPM SBP of 4 mm Hg between Week 12 and Week 24.
3. The standard deviation of the change is 15 mm Hg for both the active and placebo groups.
4. The two-sided significance level is 0.05.

A sample size of 254 per arm is required for the measurement to have 85% power to attain significance for the second primary endpoint. It is estimated that 75% of subjects will have completed the 36 weeks of study treatment since the first randomization. Thus a total sample size of 680 subjects is planned for the first randomization. It is estimated that approximately 8% will drop out for the first 12 weeks. A sample size of 626 subjects at the end of the first 12 weeks will provide >95% power for the first primary endpoint.

An interim non-binding futility analysis when half (i.e., 300) of subjects have completed the first 12 weeks of the treatment period will be conducted. Using an interpolated spending function of Type II error, i.e., with 0.5 proportion of Type II error being spent at the interim look, the study may stop for futility when the test statistic (Z score) is less than 0.656 (or p-value > 0.512). The overall power for the first primary endpoint remains >95% with this interim look. The futility boundary of this study is non-binding, meaning that the Type I error is properly controlled even if the study is continued after the futility boundary is crossed at the interim analysis.

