## 9.8 Interim Analysis

An interim non-binding futility analysis when approximately half patients completed the first 12 weeks of study 603A will be conducted. Using interpolated spending function of Type II error, i.e., with 0.5 proportion of Type II error being spent at the interim look, the study may stop for futility when the test statistics (Z score) is less than 0.656 (or p-value > 0.512). The overall power for the first primary endpoint maintains > 95% with this interim look. The interim analysis will be conducted by an independent data monitoring group.

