6. GENERAL ASPECTS FOR STATISTICAL ANALYSIS

6.1. GENERAL METHODS

Statistical methodology and analyses are in accordance with the principles outlined by the ICH E9 guidelines. All statistical analyses will be conducted using SAS statistical software version 9.3 or higher.

Tables, listings and figures (TLFs) will be produced in accordance with the principles outlined by the ICH E3 guidelines. For most summary statistics, data will be analyzed by the following treatment groups: Bexagliflozin 20 mg; Placebo. For 603B, unless otherwise specified, data will be analyzed by treatment in the 603B withdrawal period. Treatment in 603B withdrawal period will be further split by treatment sequence (as shown in Table 2). For integrated analyses, unless otherwise specified, summaries will be by total of all patients in the analysis set.

Data summaries will use descriptive statistics (number of subjects [n], mean, standard deviation [SD], Q1, median, Q3, minimum and maximum) for continuous variables, and frequency and percentage of subjects for categorical and ordinal variables, unless otherwise specified.

Unless otherwise specified, all statistical tests will be two-tailed using a 0.05 level of significance. All confidence intervals (CIs) will be two-sided 95% CIs.

Only scheduled visits will be included in by visit summaries. All visit assessment data will be included in shift tables and will appear in the subject listings.

No data imputation will be applied for missing values in safety analysis. Efficacy data imputation method will be described in Section 8.

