8. EFFICACY

Changes from baseline for efficacy data will be calculated as the post-treatment value minus the corresponding defined baseline (see Section 6.2.1). Descriptive summaries will be presented for observed and change values by treatment and visit. Assessment of proportion data will be presented by frequency and proportion by treatment and visit.

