10. INTERIM ANALYSIS

An interim non-binding futility analysis when half (i.e., 300) patients have completed the first 12 weeks of the treatment period was conducted. Using an interpolated spending function of Type II error, i.e., with 0.5 proportion of Type II error being spent at the interim look, the study could have stopped for futility when the test statistics (Z score) was less than 0.656 (or p-value > 0.512). The overall power for the first primary endpoint was maintained at >95% with this interim look. The interim analysis was conducted by an independent group that was not part of the study management team. All study subjects were to continue to receive the investigational products during the data cleaning and analysis time. Results from the interim analysis were reviewed by an independent Data Monitoring Committee (DMC). The data extraction and transfer methods and measures for preservation of blinding/access to interim results followed the rules described in the DSMB SAP.

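### The 603A futility rule treats Z < 0.656 and p > 0.512 as the same condition, but the p form leaves out every interim result at or below Z = -0.656, where bexagliflozin looks worse than placebo

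*SAP*

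**What the plan says.** The rule appears five times: in the protocol Synopsis (Statistical Methods), protocol sections 9.2 and 9.8, and SAP sections 3.7 and 10. SAP 3.7 states that "the study may stop for futility when the test statistic (Z score) is less than 0.656 (or p-value > 0.512"). Protocol 9.8 has "test statistics (Z score) is less than 0.656 (or p-value > 0.512"), and SAP 10 repeats it in the past tense: "test statistics (Z score) was less than 0.656 (or p-value > 0.512").

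SAP 3.7 sets the timing: "An interim non-binding futility analysis when half (i.e., 300) of subjects have completed the first 12 weeks of the treatment period will be conducted". It describes the boundary as coming from a spending function, "with 0.5 proportion of Type II error being spent at the interim look", and adds: "The futility boundary of this study is non-binding, meaning that the Type I error is properly controlled even if the study is continued".

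None of the five places says whether 0.512 is one-sided or two-sided, or which sign of Z favours bexagliflozin. The nearest general statements are in the SAP. Section 6.1 says: "Unless otherwise specified, all statistical tests will be two-tailed using a 0.05 level of significance". Section 8 defines change in efficacy data as "calculated as the post-treatment value minus the corresponding defined baseline".

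**The concern.** A futility rule for a superiority claim should cover weak results and adverse ones alike, because a drug that looks worse than placebo is at least as unlikely to succeed as one that looks equal to it. The Z form does this. A two-sided p-value has no direction: it is large only when the two arms look alike, and it becomes small again when the active arm does badly. An analyst who applied the p form would report the boundary as not crossed at Z = -2, and an analyst who applied the Z form would report it as crossed.

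What is at stake is whether the monitoring committee is told that the boundary was met. The error is easy to miss because the two forms agree almost exactly under the planning assumption, where a power check is made. They part company at no effect and at harm, which are the cases a futility rule is for.

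**Working it through.** **Inputs.** Boundary 0.656 and p 0.512 (SAP 3.7). Interim at 300 completers (SAP 3.7), taken as 150 per arm from the 1:1 allocation (SAP 3.8.1). SD of change 15 mm Hg in both arms, planned benefit 5 mm Hg, 626 subjects at week 12 (SAP 3.7). Below, d is the true excess reduction on bexagliflozin, and positive Z means benefit.

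**Step 1: reproduce the plan's p-value.**
- Two-sided: 2 × (1 - Φ(0.656)) = 0.5118, which rounds to 0.512.
- One-sided: 1 - Φ(0.656) = 0.2559.

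Only the two-sided value matches. The number is correctly calculated at the boundary point itself.

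**Step 2: compare the regions.** Two-sided p > 0.512 is the band |Z| < 0.656. The Z form is the half-line Z < 0.656. They differ on all Z ≤ -0.656. The standard error of the difference is 15 × √(4/300) = 1.732 mm Hg, so:
- Z = -1 is 1.73 mm Hg worse than placebo, with p = 0.317.
- Z = -2 is 3.46 mm Hg worse, with p = 0.046.
- Z = -3 is 5.20 mm Hg worse, with p = 0.003.

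Each of these meets Z < 0.656 and none meets p > 0.512.

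**Step 3: chance of meeting the rule.**
- Z form: Φ(0.656 - d/1.732).
- p form: Φ(0.656 - d/1.732) - Φ(-0.656 - d/1.732).

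| True effect | Z form | p form |
|---|---|---|
| 5 mm Hg benefit (planned) | Φ(-2.231) = 0.0128 | 0.0128 - 0.0002 = 0.0127 (unrounded terms) |
| None | Φ(0.656) = 0.7441 | 0.7441 - 0.2559 = 0.4882 |
| 3 mm Hg worse (illustrative) | Φ(2.388) = 0.9915 | 0.9915 - 0.8590 = 0.1325 |

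**Step 4: power.** Without the look, 313 per arm gives 0.986. With the rule Z < 0.656 at 300 completers followed as if binding, the bivariate normal calculation (correlation √(300/626)) gives 0.977. The stated power above 95% holds.

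**Step 5: where the boundary comes from.** The plan does not state the total type II error that was spent, so this step rests on trial values. Spending half of 0.025 at half the information gives a lower boundary of 0.647. Spending half of 0.05 at 300/626 of the information gives 0.652. Both are close to 0.656, so the Z boundary itself looks sound. This check cannot prove which region was intended, because under the planned benefit the two regions differ in probability by only 0.0002.

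**The case against.** **Nothing is miscalculated, and the Z score comes first.** This is true. The figure 0.512 is the right two-sided p-value for 0.656, and two-sided is the SAP's default. The Z form leads in all five places and is the natural operative rule. But the parenthesis offers the p-value as an alternative form of the rule, and that alternative is a different region.

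**The middle band could be deliberate.** Some two-sided designs do stop only when |Z| is small. If that were the intention, the Z form would be the wrong one, because it is printed without a lower limit. The two forms would still conflict.

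**The practical weight is small.** Most of this stands. The boundary is non-binding, an independent group ran the analysis, and an independent committee reviewed it. Protocol 3.1.3 also has the committee review unblinded safety data about every two months, with power to recommend early stopping. A committee shown bexagliflozin doing worse would not depend on a parenthesis. The case of 3 mm Hg worse is an illustration; protocol 1.1.2 reports earlier placebo-corrected reductions of 6 and 7 mm Hg.

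**The look is over.** SAP 3.8.2 and 10 describe it as conducted, under procedures in a separate monitoring-board SAP that is not among these documents. That plan may define the statistic and its direction. Nothing here shows that the p form was used.

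**A stronger reading that does not hold.** Since change is post-treatment minus baseline, a reader might infer that Z is negative when the drug works, so that a strong benefit would count as futile. The documents do not support this. SAP 3.7 words the planning effect as a positive excess reduction on bexagliflozin. With the opposite sign, the planned benefit would cross the boundary with probability Φ(0.656 + 2.887) = 0.9998, which cannot be squared with the power above 95% claimed in the same paragraph. SAP 8 defines change for efficacy data and does not define the interim statistic. An explicit sign is still worth adding, for clarity only.

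**Conclusion.** The point holds as a mis-stated decision threshold. The p form omits the region Z ≤ -0.656, which has probability 25.6% under no effect (74.4% against 48.8%). The gap widens if the drug is worse: 99.2% against about 13% at 3 mm Hg worse. Under the planned benefit the forms agree at about 1.3%, and neither the type I error nor the planned power is affected.

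These figures assume 150 subjects per arm, an SD of 15 mm Hg and a normal test statistic, and they read 0.512 as two-sided. That reading is inferred from the arithmetic and the SAP's default, because the text beside the number does not say. The covariate-adjusted analysis may have a smaller standard error. That would change the stop probabilities away from the null, but not the mismatch.

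Two further inferences should be avoided. This is not the only efficacy threshold in the programme, since both primary endpoints are tested at a two-sided 0.05. And the documents give no ground for saying that the interim decision itself was wrong.

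**What to change.** In the protocol Synopsis, protocol 9.2 and 9.8, and SAP 3.7 and 10, delete the parenthesis or replace it with *one-sided p > 0.256, in the direction of benefit*. Add one clause saying that Z is the reduction on bexagliflozin minus the reduction on placebo, divided by its standard error, so that positive Z favours bexagliflozin. If the band |Z| < 0.656 was in fact intended, the Z form would have to be restated with its lower limit instead.

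Because the look has been done, record in the study report which form and which sign convention were applied and presented to the committee.

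The cost is one phrase in each of five places and one sentence in the report. The data, the sample size and the Z boundary do not change.
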